Appendix 6: Study end points

Participation in the study will end with any one of the following events and participants will go on to have routine clinical assessments to evaluate the need for LTBI or active TB treatment.

1. 2 year follow up completed
2. Changes in chest radiography (airspace shadowing or lymphadenopathy) consistent with progressive/active TB with at least one yes answer in the symptom questionnaire.
3. Two yes answers in the symptom questionnaire.

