Transcriptional profiling of TST biopsies in LTBI patients with longitudinal follow up to identify immune response correlates of subsequent progression to active TB. This approach necessitates the ability to exclude active TB in patients at the time of TST challenge, to safely defer LTBI treatment, and to accurately identify individuals progressing to active TB before the onset of clinical disease. Blood transcriptomic biomarkers achieve these aims. They have been shown to accurately discriminate active pulmonary and extrapulmonary TB from LTBI or other infectious diseases²⁴. Blood transcriptomic changes can also predate diagnosis of active disease²⁵. Unpublished data has also shown that blood transcriptional signatures can identify patients who develop symptomatic active TB within 3 months, with positive and negative predictive values of 0.99-1 assuming cumulative 5% pre-test probability of progression to active disease in cohorts of TB contacts^{10,26}.

Twin studies indicate that the risk of active TB has a host genetic component. Candidate gene association studies focussing on innate immune responses have reported putative TB susceptibility loci⁴⁰⁻⁴⁹. Given the complexity of integrated innate and adaptive cell-mediated immunological systems, these studies do not offer the comprehensive approach required to identify the constellation of genetic polymorphisms that may affect TB risk. Conventional genome-wide association studies (GWAS) of active TB have not replicated the findings of candidate gene studies and generally lacked sufficient power⁵⁰⁻⁵⁵. Expression quantitative trait loci (eQTL) studies, in which genome-wide single nucleotide polymorphisms (SNPs) are associated with quantitative differences in transcriptional responses to a stimulus offer substantially greater power to identify the genetic correlates of variation in immune responses⁵⁶⁻⁵⁹. They also provide the fundamental advantage of directly

identifying the functional impact of genetic polymorphisms on both specific molecules and molecular pathways. An eQTL study of TST transcriptional responses offer an important opportunity to identify the genetic correlates of variation in anti-Mtb immune responses.

3. Objectives

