3.2. Secondary Objectives

- Identification of host-genetic polymorphisms associated with transcriptional variation in the TST.
- In vitro functional validation of eQTL associations and investigation of how they impact on Mtb growth in macrophages.
- To test whether expression of a whole blood transcriptional biomarker for subclinical TB resolves with LTBI therapy (LTBI treatment sub-study).

4. Study design

This is an observational study incorporating longitudinal cohort and cross-sectional components. 400 participants will be recruited to the longitudinal cohort with two year follow up, to identify TST immune responses that increase the risk of active TB (primary objective). Cross-sectional analysis of data from these 400 participants will be combined together with the data obtained from an additional 600 participants, giving a sample size of 1000 recruited over four years in total, to identify host-genetic polymorphisms associated with transcriptional variation in the TST. In vitro functional validation of eQTL associations and investigation of how they impact on Mtb growth in macrophages will be conducted in peripheral blood cells collected from selected participants. Finally, a subset (n=80) of these 1,000 participants who express a blood transcriptional biomarker for subclinical TB will be enrolled in a parallel cohort study, to test whether resolution of biomarker expression is expedited by LTBI therapy. These individuals will be offered treatment for LTBI as per national guidance, but we know that only approximately 40-60% accept this treatment. All patients will be followed up with interval blood sampling. Expression of the 3 gene biomarker will be compared at 4, 8, 12 and 24 weeks between individuals who accept and decline treatment.

5. Study schedule

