9.1. Sample size and statistical power

We will recruit 400 LTBI contacts of active pulmonary TB cases to address the primary objective. This sample size is derived from estimated progression from LTBI to active TB within 2 years of 5%, giving 20 progressors and 380 non-progressors. Progressive disease may be due to a range of different immune responses, and each variation may only be evident in a subset of cases. Therefore, conventional differential gene expression analysis in the TST between groups of progressors and non-progressors, may not identify statistically significant differences. Instead, we will undertake supervised outlier profile analysis to identify gene expression among subsets of progressors, which lies outside the normal range measured in non-progressors. These methods provide robust statistical confidence by incorporating multiple testing corrections³²⁻³⁶, and have been successfully applied to discovery of novel oncogenic pathways^{32,37}. Using preliminary TST transcriptomic data from HIV negative individuals in computational simulations, we estimate >0.8 statistical power in this sample size to detect significant outlier traits among progressors (false discovery rate <0.05) when the outlier trait is shared by 5 or more progressors (Figure 2A). In order to identify eQTLs of TST transcriptomic data, we estimate that a sample size of 1000 is required to give >90% power to detect statistically significant correlations ($p < 10^{-8}$) for allelic frequencies $\geq 5\%$ depending on the correlation coefficients, as a composite measure of effect size and variance⁶¹. Finally, from our pilot data, we estimate that 15% of these individuals will express the blood transcriptional biomarker at time of recruitment to the study. Of these estimated 150 participants, 80 will be recruited to the LTBI treatment sub-study. Conservatively assuming that only 25% of patients decline LTBI therapy, a sample size of 68 participants will provide 80% power to detect a difference of 0.8 standard deviations (SDs) in signature scores between those who accept and decline treatment at each time point. This calculation assumes similar standard deviations among individuals in both groups. We have estimated 0.8SDs as the minimum difference in signature scores that is likely to be of clinical significance (based on the difference in mean scores between IGRA-positive and IGRA-negative TB case-contacts in our pilot data. To allow for losses to follow-up, 80 participants will be recruited.

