Longitudinal study follow up assessments (mark with tick or cross)			Outcome (circle)
3 months		Persistent cough for more than two weeks?	Continue Treatment study End study
Blood	Weight loss in the last 3 months?		
CXR	Drenching night sweats during the last 3 months?		
6 months		Persistent cough for more than two weeks?	Continue Treatment study End study
Blood	Weight loss in the last 3 months?		
CXR	Drenching night sweats during the last 3 months?		
9 months		Persistent cough for more than two weeks?	Continue Treatment study End study
Blood	Weight in the last 3 months?		
CXR	Drenching night sweats during the last 3 months?		
12 months		Persistent cough for more than two weeks?	Continue Treatment study End study
Blood	Weight loss in the last 3 months?		
CXR	Drenching night sweats during the last 3 months?		
15 months		Persistent cough for more than two weeks?	Continue Treatment study End study
Blood	Weight loss in the last 3 months?		
CXR	Drenching night sweats during the last 3 months?		
18 months		Persistent cough for more than two weeks?	Continue Treatment study End study
Blood	Weight loss in the last 3 months?		
CXR	Drenching night sweats during the last 3 months?		
21 months		Persistent cough for more than two weeks?	Continue Treatment study End study
Blood	Weight loss in the last 3 months?		
CXR	Drenching night sweats during the last 3 months?		
24 months		Persistent cough for more than two weeks?	Continue Treatment study End study
Blood	Weight loss in the last 3 months?		
CXR	Drenching night sweats during the last 3 months?		
Notes			

LTBI treatment study follow up assessments (mark with tick or cross)				Outcome (circle)
4 weeks		Persistent cough for more than two weeks?		Continue End study
Blood		Weight loss in the last 3 months?		
		Drenching night sweats during the last 3 months?		
Missed doses in last 4 weeks?			Pill count?	
8 weeks		Persistent cough for more than two weeks?		Continue End study
Blood		Weight loss in the last 3 months?		
		Drenching night sweats during the last 3 months?		
Missed doses in last 4 weeks?			Pill count?	
12 weeks		Persistent cough for more than two weeks?		Continue End study
Blood		Weight in the last 3 months?		
		Drenching night sweats during the last 3 months?		
Missed doses in last 4 weeks?			Pill count?	
24 weeks		Persistent cough for more than two weeks?		Continue End study
Blood		Weight loss in the last 3 months?		
		Drenching night sweats during the last 3 months?		

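### LTBI treatment sub-study: Appendix 6 and the CRF stop participation at a symptom end point, section 4 says everyone keeps being sampled, and the scores lost would be related to the outcome

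*Protocol*

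**What the plan says.** - **Section 4 (Study design)** describes the sub-study as a parallel cohort of biomarker-positive participants. It says "All patients will be followed up with interval blood sampling" and "Expression of the 3 gene biomarker will be compared at 4, 8, 12 and 24 weeks between individuals who accept and decline treatment".
- **Appendix 6** says "Participation in the study will end with any one of the following events". The events are completion of two years, radiographic change with at least one positive symptom answer, and "Two yes answers in the symptom questionnaire". It does not say whether sub-study participants are covered.
- **Appendix 11 (CRF)** repeats the same three symptom questions at sub-study weeks 4, 8, 12 and 24, with blood at each visit and the outcome choice "Continue End study". No radiograph field appears on the sub-study pages.
- **Section 9.1** gives the size: "Conservatively assuming that only 25% of patients decline LTBI therapy, a sample size of 68 participants will provide 80% power" for a 0.8 SD difference at each time point. Its only provision for missing scores is "To allow for losses to follow-up, 80 participants will be recruited".
- **Section 2** describes blood signatures of this kind as able to "identify patients who develop symptomatic active TB within 3 months".
- **Section 9.2** plans linkage to national surveillance records. That recovers who progressed, not anyone's biomarker score.

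**The concern.** Section 4 cannot hold for anyone whose participation ends early under Appendix 6, so a site does not know whether to keep drawing blood.

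The choice affects the estimate as well as the count. The sub-study outcome is a marker of subclinical TB, and the exit trigger is symptoms of TB. Someone whose marker stays high is more likely to reach the trigger, and if therapy works this should happen more often in people who declined it. The later decliner mean would then rest on decliners who did not become symptomatic. A real accept/decline difference would look smaller, and spontaneous resolution would look commoner.

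An analysis plan can set a rule for such participants, but it cannot supply samples that were never taken. This therefore has to be settled in the protocol.

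**Working it through.** **1. Does the stop operate inside the sub-study?** Appendix 6 is the only text that says when symptom answers end participation. The sub-study CRF asks for those answers and offers an end-of-study outcome at all four visits. Radiographs are not listed on those pages, so the two-symptom rule is the main trigger there. Read together, the stop can operate. Read with section 4, it should not.

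**2. The plan's own figures.** Inputs from section 9.1: difference 0.8 SD, equal SDs (set to 1), 25% declining (three accepters per decliner), 80% power. Alpha is not stated; two-sided 0.05 is assumed.

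- Decliners needed: (1 + 1/3) × (1.960 + 0.842)² / 0.8² = 1.333 × 7.849 / 0.64 = 16.35, so 17. With 51 accepters the total is 68.
- Check by noncentral t: 0.8 / √(1/17 + 1/51) = 2.857 on 66 df, power 0.804.
- Allowance: 12/80 = 15%, and 68 / 0.85 = 80.

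Both 68 and 80 reproduce. With all 80 sampled (20 v 60), noncentrality is 0.8 / √(1/20 + 1/60) = 3.098 on 78 df, power 0.864.

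**3. Exits related to score.** Let a share p of decliners exit, with correlation ρ between exit propensity and the person's own score (normal, SD 1, higher meaning more disease). The mean of those remaining falls by ρ × φ(z) / (1 − p), where z is the (1 − p) normal quantile.

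- p = 0.05: 0.1031 / 0.95 = 0.109
- p = 0.10: 0.1755 / 0.90 = 0.195
- p = 0.20: 0.2800 / 0.80 = 0.350

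The shift is halved at ρ = 0.5. Power below is from simulated pooled t-tests, 20 v 60, true difference 0.80 SD, exits among decliners only.

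| Decliners exiting (assumed) | Expected difference, ρ = 0.5 to 1 | Power, ρ = 0.5 to 1 |
|---|---|---|
| 0% | 0.80 SD | 0.86 |
| 5% | 0.75 to 0.69 SD | 0.81 to 0.76 |
| 10% | 0.70 to 0.61 SD | 0.74 to 0.65 |
| 20% | 0.62 to 0.45 SD | 0.60 to 0.37 |

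**4. Selection or numbers?** If 15% of decliners leave for reasons unrelated to score, the expected difference stays at 0.80 SD and power is 0.82. The allowance covers that case. It does not cover score-related exit.

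**5. Direction.** At p = 0.15 the full shift is 0.2332 / 0.85 = 0.274. If exits are equally frequent and equally score-related in both groups, the shifts cancel and 0.80 SD remains. If only accepters exit (ρ = 0.5), the difference rises to 0.80 + 0.137 = about 0.94 SD.

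**6. Which visits?** Blood is scheduled at every sub-study visit, so a person ended at week 12 can still give a week 12 score; only later scores are lost. Three months is close to week 12, so on section 2's timing the loss falls mainly on week 24. Exits at week 4 or 8 would also reach weeks 8 and 12.

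**7. What the protocol implies about the exit rate.** Section 9.1 has 5% of contacts progressing over two years and 15% biomarker-positive. Even if every progressor were positive at entry, that is 5/15, about one third of positives, over a period much longer than 24 weeks. Section 2's predictive value of 0.99–1 within three months would imply far more. Neither figure is an exit rate for this sub-study, so the range in step 3 is an assumption.

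**The case against.** The strongest reply is that Appendix 6 was written for the two-year cohort. Its first event is completion of two years, its second needs a radiograph that the sub-study pages do not list, and section 5 uses it to define progressors before two years. Section 4 says plainly that everyone is followed. Handling of participants who develop TB is also normally left to the SAP, which is not at hand. This is fair as far as it goes: it shows ambiguity, not a settled rule removing progressors. It does not explain why the sub-study CRF repeats the same questions with an end-of-study outcome, and it does not recover samples not taken.

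Three stronger readings are tempting and are not supported:

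- **That the protocol counts these participants as ordinary losses.** It is silent on how they enter the comparison. The increase from 68 to 80 is a sample-size allowance, not an analysis rule.
- **That the treatment effect is masked.** Attenuation is the likely direction, but its size depends on an unstated rate and is small at 5%. The trigger is unconfirmed self-report, which accepters can also meet.
- **That power collapses.** A reader might remove further decliners from 17 v 51 and assume that exit tracks score perfectly. But 17 v 51 is already net of the loss allowance, and perfect correlation is an extreme for two symptom answers. The 25% declining is also deliberately conservative. Section 4 expects 40–60% to accept; at 40 v 40, power is about 0.86 to 0.80 with 10% exit and 0.76 to 0.54 with 20%, against 0.94 with none.

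**Conclusion.** The point holds as an internal contradiction with a statistical consequence. Section 4 on one side, and Appendix 6 with the sub-study CRF on the other, give incompatible answers on whether sampling continues after a symptom end point. If the stop is applied, scores after exit are missing for reasons related to the outcome and plausibly to the group, and enlarging the sample does not correct that.

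The size is conditional: between 5% and 20% decliner-only exit, the expected 0.80 SD falls to somewhere between 0.75 and 0.45 SD, with power between 0.81 and 0.37 instead of 0.86. This rests on an assumed exit rate, correlation of 0.5 to 1 between exit and score, two-sided 0.05, and a 25:75 split of all 80. The sign is likely but not assured. The point concerns a secondary objective and does not affect the section 9.1 arithmetic.

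**What to change.** Reconcile section 4, Appendix 6 and the sub-study pages of Appendix 11 by stating, for the LTBI treatment sub-study:

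1. Reaching an Appendix 6 end point does not stop the scheduled research blood samples at the remaining visits, subject to consent.
2. The Tempus sample is taken at the visit where the end point is met.
3. The date on which any TB treatment starts is recorded, because a decliner's scores after that date are no longer untreated scores.
4. The accept/decline comparison uses all available scores. One pre-stated supportive analysis ranks participants diagnosed with active TB as worst (not resolved) at later time points.

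The supportive analysis should depend on a diagnosis of active TB, not on two symptom answers. Making unconfirmed symptoms a failure in the main comparison would replace a measured biomarker with a clinical composite and could rank someone whose marker had resolved as worst.

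The cost is protocol and CRF wording, a few further samples that are already on the schedule, and one extra analysis. Clinical assessment, referral and treatment decisions are unchanged.

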Participants who request to withdraw from the study or are lost to follow up will be referred back to the routine clinical service by the study team. Participants who develop a positive blood transcriptional biomarker at any point during longitudinal follow-up will then enter the LTBI treatment sub-study. Participants who develop a positive blood transcriptional biomarker or reach a study end point (Appendix 6) as a surrogate for progressive TB before 2 years, will be identified as progressors. Participants who complete 2 years follow up will be identified as non-progressors. Progressors and non-progressors will undergo routine clinical assessments to evaluate the need for any TB treatment when their participation in the study ends.

6. Recruitment and consent

Potential participants who meet the eligibility criteria will be identified by the routine tuberculosis clinical service and introduced to the study team. The study team will describe the study to these individuals, provide them with the participant information sheet, and answer their questions, in person, by telephone, by post or by email according to the participant's preferences. After at least 24 hours to consider this information, the study team will invite those who agree to participate to provide written informed consent.

For non-English speakers the study team will communicate with telephone translation services and provide translations of the participant information sheet and consent form. The original signed consent form will be filed in the study master file and a copy will be provided to the participant. All participants who are referred to the study team will be entered into a screening log with a record of their eligibility criteria, their decision to participate or reasons for declining to participate as appropriate.

7. Eligibility criteria

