7.2. Exclusion Criteria

- Age <18 or >60 years
- Unable to give written consent
- Clinical or radiographic features of active tuberculosis
- HIV-1 infection
- Active hepatitis B or C infection
- Pregnancy
- History of autoimmune disease
- History of skin disease
- History of malignancy
- Immunomodulatory drugs (Appendix 6)
- History of allergy to local anaesthetics
- History of keloid scarring

8. Clinical governance and indemnity

The risks for participants in the present study are summarised in Appendix 8.

Participants' General Practitioners will be notified of their patient's involvement in this study, subject to written informed consent by the patient.

All participants will be contacted 1 week after their final visit to check that the TST biopsy wounds have healed as expected. Where necessary, participants will be offered a further appointment for clinical review of the biopsy sites and to instigate appropriate clinical management under the supervision of the Chief Investigator.

Any participants who develop evidence of active tuberculosis will be referred for urgent review by routine clinical TB services.

All adverse events will be recorded as described in Appendix 9. All complaints and adverse events will be reported immediately to the sponsor by email ([contact]) and using the on line incident reporting form (<https://opinio.ucl.ac.uk/s?s=17671>). If the adverse event takes place within a UCLH Trust site, the event will be reported through the Trust incident reporting system (Datix). Annual progress reports will be submitted to the Research Ethics Committee.

University College London holds insurance against claims from participants for harm caused by their participation in this clinical study. Participants may be able to claim compensation if they can prove that UCL has been negligent. However, if this clinical study is being carried out in a hospital, the hospital continues to have a duty of care to the participant of the clinical study. University College London does not accept liability for any breach in the hospital's duty of care, or any negligence on the part of hospital employees. This applies whether the hospital is an NHS Trust or otherwise.

9. Statistical methods

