Appendix 9: Risks to participants

Severity score- Low=can cause discomfort but unlikely to have an impact on health, Moderate=potential impact on health but unlikely to be life-threatening, Severe=definite impact on health and significant potential to be life-threatening.

Description of risk	Estimated incident rate	Severity	Justification
Progressive active TB as a result of deferring LTBI treatment in the longitudinal study.	<1%	Moderate	The two year cumulative risk of progressive TB in individuals being recruited to this study (IGRA positive contacts of active pulmonary TB) is estimated to be 5%. In routine clinical practice LTBI treatment is commonly offered to all such individuals. On the basis that this treatment is in fact not necessary for the vast majority, clinical review at 3-6 monthly intervals is widely used as an alternative approach. In the present study, we will undertake enhanced follow up at 3 monthly intervals with the addition of novel blood biomarkers with the potential to identify subclinical active TB representing an end point in their participation, when individuals will be offered treatment in line with standard clinical care. The available data on the predictive value of these biomarkers indicates that this approach minimises the 2 year cumulative risk of the development of symptomatic TB disease <1%. On the basis subclinical active TB will not meet conventional criteria for the diagnosis of symptomatic TB disease requiring full TB treatment, we expect that most participants who develop biomarkers of subclinical TB will be offered LTBI treatment. On the basis of being IGRA positive, all participants who complete 2 year follow up will be considered for LTBI treatment as per routine clinical practice. The risk of active TB is substantially lower after 2 years follow up, therefore these participants may opt not to accept LTBI treatment.

Description of risk	Estimated incident rate	Severity	Justification
Increased radiation exposure due to repeated chest radiographs	100%	Low	Participants may have up to 8 extra chest radiographs. Each of these is equivalent to 10 days of natural background radiation exposure, associated with a negligible additional cancer risk of <0.01%. This risk is substantially outweighed by the benefits of chest radiographic monitoring for evidence of progressive TB.
Discomfort during phlebotomy	10%	Low	The overall risk of harm is very low.

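### A participant with a TB-consistent follow-up film, no symptoms and a persistently negative biomarker is labelled a non-progressor at 2 years, and nothing stated corrects the label

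*Protocol*

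**What the plan says.** Appendix 6 lists three events that end participation: "2 year follow up completed"; "Changes in chest radiography (airspace shadowing or lymphadenopathy) consistent with progressive/active TB with at least one yes answer in the symptom questionnaire"; and "Two yes answers in the symptom questionnaire". The questionnaire in Appendix 5 has three questions.

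Section 5 turns these events into the outcome. "Participants who develop a positive blood transcriptional biomarker or reach a study end point (Appendix 6) as a surrogate for progressive TB", if this happens before 2 years, are progressors. Then: "Participants who complete 2 years follow up will be identified as non-progressors".

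Other places treat a radiographic sign differently:
- Section 7.2 bars entry for "Clinical or radiographic features of active tuberculosis"; either kind is enough.
- Section 8 sets no symptom condition: "Any participants who develop evidence of active tuberculosis will be referred for urgent review by routine clinical TB services". It says nothing about study status or the progressor label.
- Appendix 9 allows up to 8 extra films and justifies them: "This risk is substantially outweighed by the benefits of chest radiographic monitoring for evidence of progressive TB".

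Section 9.2 adds linkage to national TB surveillance records to find progressors among cross-sectional participants and among longitudinal participants who withdraw or are lost before 2 years. Section 9.1 plans 400 longitudinal participants with 5% progression, and takes the normal range for the outlier analysis from the non-progressors.

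**The concern.** The progressor label is the outcome for the primary objective. A new film with airspace shadowing or lymphadenopathy is direct evidence bearing on that outcome, and on its own it would have kept the person out of the study at entry. In follow-up the same film, without a symptom, changes neither study status nor label. If the biomarker also stays negative, the default at 2 years is non-progressor.

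Section 8 should send that person for clinical review, but the protocol does not carry the result back into the classification. A diagnosis made by that route does not, by any stated rule, make the participant a progressor. With so few progressors planned, single labels matter: a case placed on the wrong side leaves a small group and joins the reference group against which that group is judged.

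**Working it through.** **1. The plan's own split.** Section 9.1: 400 × 0.05 = 20 progressors and 400 − 20 = 380 non-progressors. This reproduces.

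**2. Tracing the rules.** For a participant whose biomarker is negative at every visit, Appendix 6 and Section 5 give:

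| Yes answers | Film not TB-consistent | Film TB-consistent |
|---|---|---|
| 0 | no end point; non-progressor at 2 years | **no end point; non-progressor at 2 years** |
| 1 | no end point; non-progressor at 2 years | item 2; progressor |
| 2 or 3 | item 3; progressor | items 2 and 3; progressor |

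The film changes the label only in the row with exactly one yes answer. If the biomarker turns positive at any visit, the participant is a progressor whatever the row. The gap is therefore the one cell in bold, under a biomarker that stays negative.

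**3. Does another provision correct that cell?**
- Section 7.2 acts at entry only.
- Section 8 gives clinical referral and no label.
- Section 9.2 linkage covers someone who withdraws or is lost before 2 years, not someone who completes.

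For a completer, none of them does.

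**4. Effect per case.** Progressor group: 1/20 = 5%. Non-progressor group: 1/381 = 0.26%.

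**5. Range.** The documents give no frequency. Assume that 0 to 30% of the 20 progressors are film-positive, symptom-free and biomarker-negative throughout. Section 9.1 claims power above 0.8 when a trait is shared by 5 or more progressors. That figure comes from simulations shown in a figure that is not available, so it cannot be recomputed. As an illustration only, the chance that at least 5 of n labelled progressors carry a trait of prevalence t is

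P(X ≥ 5) = 1 − Σ (k = 0 to 4) C(n,k) t^k (1−t)^(n−k).

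| Assumed silent share | Progressors / non-progressors | Misplaced share of non-progressors | t = 30% | t = 40% |
|---|---|---|---|---|
| 0% | 20 / 380 | 0% | 0.76 | 0.95 |
| 5% | 19 / 381 | 0.26% | 0.72 | 0.93 |
| 10% | 18 / 382 | 0.52% | 0.67 | 0.91 |
| 20% | 16 / 384 | 1.04% | 0.55 | 0.83 |
| 30% | 14 / 386 | 1.55% | 0.42 | 0.72 |

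The trait prevalences are also assumptions. The effect runs mainly through loss from the small progressor group.

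**The case against.** The design does not rest on the film. Section 2 assigns the detection of progression before clinical disease to the blood biomarker, and Appendix 9 credits the biomarkers for keeping symptomatic TB below 1%. A symptom condition on the film can be defended as protecting specificity: with 20 expected progressors, one false-positive film also distorts that group by 5%. Entry and follow-up rules may properly differ, because a broad exclusion gives a clean baseline. All of this stands. The difference from Section 7.2 is thus not an error in itself, and the aim in Section 2 is not defeated.

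A reader might infer that symptom-free radiographic TB goes without care, or that the films bring no benefit for their radiation. The documents do not support either. Section 8 referral has no symptom condition, so the film still works as a safety monitor, and the benefit claimed in Appendix 9 can be delivered that way.

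It can also be said that someone diagnosed after referral would probably leave before 2 years and be found by linkage, and that if review excludes TB the non-progressor label is right. Both are fair and they narrow the problem. But no passage says that a diagnosis through Section 8 ends participation or sets the label, and a completer is outside the linkage as described. Section 4 does use the 400 in the cross-sectional analysis, which might suggest wider linkage. Section 9.2, however, names longitudinal withdrawals and losses separately, which would be needless if completers were included.

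The case record form has no dedicated field for the film result. It does have a tick-or-cross entry, an outcome choice and notes for the longitudinal visits, so this does not show that results go unrecorded.

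**Conclusion.** The concern holds as a gap in outcome classification. It needs three things together: a new TB-consistent film, no yes answers and a biomarker that stays negative, in someone who completes 2 years. The written rules then give a non-progressor label even if clinical review found TB.

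Its size is 5% of the planned progressors and about 0.26% of the non-progressors per case. The number of such cases is unknown; the 0 to 30% range above is an assumption. It may be zero.

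Two stronger readings should be resisted. One is that the normal range in non-progressors would be spoiled: even at the 30% assumption only 1.55% of that group is misplaced. The other is to count the visits at which a film could be decisive. If each question is answered yes independently at 2% to 10% of visits, exactly one yes occurs at 3p(1−p)² = 5.8% to 24.3% of visits. That rests on assumed symptom rates and describes visits, mostly by people without TB; it does not count misclassified participants.

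Severity is moderate. One limit: the content of the schedule in Appendix 2a is not in the text available, so a rule given only there would not have been seen.

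**What to change.** Reconcile Section 5, Section 8, Appendix 6 and Appendix 9 so that one statement says how two events affect study status and the progressor label: a TB-consistent film without symptoms, and a TB diagnosis made through Section 8 referral. Which clinical rule applies is for the sponsor and investigators.

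For the analysis, whichever rule they choose:
- do not count a participant with a TB-consistent film as a non-progressor until the outcome of the Section 8 review is recorded;
- extend the Section 9.2 surveillance linkage to participants who complete 2 years.

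The cost is amendment wording and a little more data work. No new films are needed. A few classifications would be delayed or changed.
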